### **9.1.8 Physical Examination**

The physical exams must be performed by the PI or designee (or a licensed medical practitioner such as a physician's assistant or nurse practitioner) listed on the site delegation of authority log.

A complete physical examination includes the following assessments: general appearance, head, eyes, ears/nose/throat, neck, lymph nodes, skin, lungs, heart, abdomen, musculoskeletal, and neurologic evaluations. If the subject is discontinued for any reason during the treatment phase, every attempt should be made to perform a final physical examination.

### **9.1.9 Vital Signs**

Arterial systolic and diastolic blood pressure and radial artery pulse rate will be measured while the patient is seated at the scheduled visits designated in the Schedule of Events in Appendix 1.

#### **9.1.9.1 Height and Body Weight**

Height will be measured at the screening visit. Patients will be measured without shoes. Body weight will be recorded at screening, baseline and every visit through the 9-week treatment phase.

#### **9.1.9.2 Body Mass Index (BMI)**

Body mass index (BMI) will be determined with the patient's height and weight at the screening visit and subsequent treatment visits. BMI must be calculated using the following formula: A person's (Weight in pounds divided by their height in inches squared)  $\times 703$ .

#### **9.1.9.3 Waist and Hip Circumference**

Waist and hip circumference will be recorded at screening, baseline, and all study visits.

### **9.1.10 Electrocardiogram (12-Lead ECG)**

The PI or a physician listed on the site delegation of authority log must review, initial, and date the report, which must be filed in the subject's study chart. Results will be captured in the subject's study chart, not in the electronic database. Clinically significant findings from the screening report must be captured in the medical history. Eligibility for study entry must be assessed by the principal investigator. Any clinically significant changes compared with baseline must be captured as AEs in the electronic database.

Subjects are to be supine for at least 5 minutes prior to ECG assessments. A central facility will be used in this study for interpretation and analysis of ECGs. All subjects will have standard resting 12-lead ECGs performed and interpreted. The time the ECG is performed will be recorded (using a 24-h clock). In addition, the time that the subject took their last dose of study medication (prior to the ECG) will be recorded on the CRF page.

### **9.1.11 Adverse Event (AE) Monitoring**

The PI or a designee (eg, a licensed, qualified medical practitioner such as a physician's assistant or a nurse practitioner) listed on the site delegation of authority log must assess the severity and relationship to study medication(s) of all AEs. All observed or volunteered AEs regardless of treatment group or suspected causal relationship to the investigational product(s) will be recorded on the AE page(s) of the eCRF.

For all AEs, the investigator must pursue and obtain information adequate both to determine the outcome of the AE and to assess whether it meets the criteria for classification as an SAE requiring immediate notification to the Sponsor or its designated representative.

For all AEs, sufficient information should be obtained by the investigator to determine the causality of the AE. The investigator is required to assess causality and indicate that assessment on the eCRF. For AEs with a causal relationship to the investigational product, follow-up by the investigator is required until the event or its sequelae resolve or stabilize at a level acceptable to the investigator.

Adverse events (serious and non-serious) should be recorded on the CRF from the date the informed consent form (ICF) was signed until the end of their participation in the study, ie, the subject has discontinued or completed the study.

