### **Safety Assessments**

Safety will be evaluated with Fisher's exact tests, by comparing the following assessments between the MMFS-202-302 and Placebo groups: adverse events, laboratory test results, vital signs, body weight, and subjective remarks. The safety population will include all subjects who had at least one exposure to a study compound, and who had any subsequent encounter with the study staff.

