## 6.0 STUDY PROCEDURES

Study visits will include screening and 5 treatment visits (baseline, Weeks 1, 3, 6, and 9). Patients will be contacted by telephone at Weeks 2, 4, 5, 7, and 8 for monitoring of medication compliance, change in concomitant medication, and adverse events. Please see Appendix 1 – Schedule of Assessments.

At screening, the Structured Clinical Interview for Diagnosis for DSM Disorders (SCID) will be completed for confirmation of psychiatric diagnosis. A medical/psychiatric history will also be collected and a physical exam will be performed. Vital signs including weight, height, waist and hip measurement will be obtained at screening to record body mass index.

Subjects will be administered MMFS-202-302 at a fixed single dose of 2 grams (1 gram twice per day),

or placebo after the completion of the baseline assessments.

Methods:

- A) Measurement and Treatment Research to Improve Cognition in Schizophrenia (MATRICS) battery, including some supplemental cognitive assessments (FAS, ACT, WCST)
- B) Positive and Negative Syndrome Scale (PANSS) for schizophrenia and schizoaffective disorder
- C) MRI assessments:
  - a. Structure: MPRAGE (T1), T2
  - b. Function: Resting connectivity
  - c. Function: Reward/aversion and attention: fMRI paradigm of IAPS (standardized images selected to be neutral, pleasurable, or arousing) and Spinner Task
  - d. Function: Capacity working memory task
- D) A set of cognitive psychological paradigms performed outside of the magnet following the MRI scan:
  - a. Keypress task for an adaptation of the International Affective Picture Set (IAPS)
  - b. A spinner wheel rating task of the reward/aversion associated with monetary gains/losses
- E) Brief Negative Symptom Scale (BNSS)
- F) Calgary Depression Scale for Schizophrenia
- G) Clinical Global Impression of Severity (CGI-S) and Change (CGI-C)
- H) Measurement of RBC Mg at baseline and end of study
- I) EEG evaluation, measuring connectivity and activation using learning and memory tests

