## 11.6 Steps to Determine If an Adverse Event Requires Expedited Reporting

Step 1: Identify the type of adverse event

Step 2: Grade the adverse event

Step 3: Determine whether the adverse event is related to the protocol therapy

Attribution categories are as follows:

- Definite – The AE is *clearly related* to the study treatment.
- Probable – The AE is *likely related* to the study treatment.
- Possible – The AE *may be related* to the study treatment.
- Unrelated – The AE is *clearly NOT related* to the study treatment.

Note: This includes all events that occur within 30 days of the last dose of protocol treatment. Any event that occurs more than 30 days after the last dose of treatment and is attributed (possibly, probably, or definitely) to the agent(s) must also be reported accordingly.

Step 4: Determine the prior experience of the adverse event.

Expected events are those that have been previously identified as resulting from administration of the agent. An adverse event is considered unexpected, for expedited reporting purposes only, when either the type of event or the severity of the event is not listed in:

- the current known adverse events listed in the Agent Information Section of this protocol;
- the GRAS dossier for the supplement;

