## 11.7 Reporting Requirements for Adverse Events

Expedited

- The Principal Investigator must be notified within 24 hours of learning of any serious adverse events, regardless of attribution, occurring during the study or within 30 days of the last administration of the study drug.
- The investigator will inform the sponsor within 24 hours of notification of any serious adverse event by phone or fax, with follow-up with a written narrative of the event within 48 hours.
- The Northwestern University Institutional Review Board must be notified within 10 business days of "any unanticipated problems involving risk to subjects or others"

The following events meet the definition of UPR:

1. Any serious event (injuries, side effects, deaths or other problems), which in the opinion of the Principal Investigator was unanticipated, involved risk to subjects or others, and was possibly related to the research procedures.
2. Any serious accidental or unintentional change to the IRB-approved protocol that alters the level of risk.
3. Any deviation from the protocol taken without prior IRB review to eliminate apparent immediate hazard to a research subject.
4. Any new information (e.g., publication, safety monitoring report, updated sponsor safety report), interim result or other finding that indicates an unexpected change to the risk/benefit ratio for the research.
5. Any breach in confidentiality that may involve risk to the subject or others.
6. Any complaint of a subject that indicates an unanticipated risk or that cannot be resolved by the Principal Investigator.

- The FDA will be notified within 7 business days of any unexpected fatal or life-threatening adverse event with possible relationship to study drug, and 15 business days of any event that is considered: 1) serious, 2) unexpected, and 3) at least possibly related to study participation.

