### **14.3 Data Management and Monitoring/Auditing**

A database in the RedCap system will be used for data entry and will be formatted to simulate the hard copy data entry forms. Once entered into this database, the data files can be extracted into Excel or SAS project databases, which are maintained on a networked directory under the direct supervision of the PI and biostatistician. Back-ups are routinely performed to assure the preservation of the database.

Data are checked for range, consistency, missing values, etc. During data analysis, combined datasets are created as needed. Data are maintained in the master system datasets using a source/derived data approach, where source datasets are maintained unmodified, while the derived datasets are modified as needed. Thus, alterations that prove to be incorrect are easily rectified. The confidentiality of all data is maintained using the HIPAA compliance standards of Northwestern University. No confidential information is posted to the web under any circumstances. All possible efforts are made to retain only the necessary information in all cases.

Regarding de-identification of the data set: No identifiable information for any subjects (i.e. name, initials or date of birth) will be collected in the analyzable RedCap database or directly linked to study data. Subjects will be coded only with study-specific unique ID numbers.

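### CRF recording of adverse events ends at study exit, but the reporting rules run to 30 days after the last dose, with no contact or stated data route to bridge the gap

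*Combined protocol and SAP*

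**What the plan says.** Section 9.1.11 sets the recording period. It opens at consent, "Adverse events (serious and non-serious) should be recorded on the CRF from the date the informed consent form (ICF) was signed", and runs "until the end of their participation in the study, ie, the subject has discontinued or completed the study". It gives no period after the last dose.

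Two later sections look beyond that point. In the steps for deciding whether an event needs expedited reporting, a note in Section 11.6 states: "This includes all events that occur within 30 days of the last dose of protocol treatment". It goes further for events judged possibly, probably or definitely due to the agent: "Any event that occurs more than 30 days after the last dose of treatment and is attributed" must also be reported, with no upper limit. Section 11.7 requires the principal investigator to be notified of any serious event, whatever its attribution, "occurring during the study or within 30 days of the last administration of the study drug".

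The contact schedule stops earlier. Section 6.0 reads "Study visits will include screening and 5 treatment visits (baseline, Weeks 1, 3, 6, and 9", with telephone calls at Weeks 2, 4, 5, 7 and 8. The last column of the Appendix 1 schedule is Day 63.

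The Safety Assessments part of Section 3.0 evaluates safety with Fisher's exact tests, "by comparing the following assessments between the MMFS-202-302 and Placebo groups: adverse events, laboratory test results" and other measures. It states no time window for adverse events. On the source of the data, Section 14.3 says: "A database in the RedCap system will be used for data entry and will be formatted to simulate the hard copy data entry forms". Analysis files are extracted from that database.

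**The concern.** The protocol commits to acting on late events but has no matching arrangement for finding or recording them. The mismatch is sharpest for serious events: Section 11.7 wants to hear of them for 30 days after the last dose, while Section 9.1.11 has by then closed the form on which they would be entered.

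The stake is the completeness of the safety data. An event that first appears shortly after the tablets stop could be missed because nobody asks. It could also be reported to the sponsor and the IRB without ever reaching the data used to compare the arms. Section 10.0 lists toxicity among the reasons for removal, so some of the patients whose recording closes early may be those in whom late harm is of most interest. The primary efficacy endpoint is not affected.

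**Working it through.** The plan states no figure on this point, so there is nothing to reproduce. The check sets the provisions side by side and then measures the gap.

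**Step 1. Windows compared.**

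| Provision | Events covered | Where it ends | Says how events reach the CRF or database? |
|---|---|---|---|
| 9.1.11 | Serious and non-serious | Study completion or discontinuation | Yes, CRF |
| 11.6, note under Step 3 | All events, within the expedited-reporting steps | 30 days after last dose; open-ended if attributed to the agent | No |
| 11.7 | Serious only | 30 days after last administration | No |
| 3.0, Safety Assessments | Adverse events compared by arm | Not stated | No |
| 6.0 and Appendix 1 | Scheduled contacts | Day 63 | Not applicable |

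Section 11.7 names the 30 days as an alternative to the study period itself, so it envisages events after participation has ended.

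**Step 2. Could a late event be detected?** No visit or call follows Day 63. Section 11.4 follows each adverse event until it resolves, returns to baseline, is otherwise explained or ends in death. That covers events already known, not new ones. Detection of a new event would depend on the patient or a treating clinician volunteering it.

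**Step 3. Could a detected event be analysed?** The documented path is CRF, then database, then Fisher's test. No section says that reports received after study exit are added to the database or reconciled with it. No section says that they are kept out either.

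**Step 4. Length of the gap.** Take dosing as running to Day 63 (the Week 9 visit), with the 30 days from Sections 11.6 and 11.7.

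- Completer: 30 / (63 + 30) = 30 / 93 = 0.32.
- Patient who stops dosing and leaves the study on Day 7: 30 / (7 + 30) = 30 / 37 = 0.81. This holds only if both happen on the same day.

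**Step 5. Illustration in patients.** The documents give no event rate, so every input here is an assumption except the 60 patients and the day counts. Let p be the proportion with a given type of event in 63 days, and let f be the hazard after the last dose as a fraction of the on-treatment hazard. With a constant hazard h = −ln(1 − p) / 63, the probability of an event in the 30 days is q = 1 − exp(−30fh).

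- p = 0.05, f = 0.25: q = 0.0061, and 60q = 0.37 patients.
- p = 0.20, f = 1: q = 0.1008, and 60q = 6.05 patients.

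Counting only patients with no such event on treatment, 60(1 − p)q runs from 0.35 to 4.84.

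**Step 6. Sensitivity of the test.** With 30 per arm, Fisher's two-sided p is 0.052 for 5 versus 0 patients and 0.024 for 6 versus 0. One patient more or less can therefore move a comparison across 0.05. This shows how sparse the data are; it does not show that any such patient would be lost.

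**The case against.** The strongest reply is that these are two duties with different end dates. Section 9.1.11 governs CRF entry, and Sections 11.6 and 11.7 govern expedited reporting. A site can close the CRF at Week 9 and still notify a serious event that occurs on Day 80. That stands: a reader might infer that the sections cannot all be followed, but they can.

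A reader might also infer that late events are shown to be missing from the arm comparison. They are not. Section 3.0 gives no window, and no section excludes late reports from the database. Section 9.1.11 also asks for every observed or volunteered event to go on the eCRF, in a sentence with no end date of its own, although the closing paragraph of the same section supplies one. The loss is an inference from silence.

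The 30-day provisions are narrow. Section 11.7 covers serious events only; for non-serious events the commitment rests on the Section 11.6 note alone.

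Nor does recording clearly stop when a patient stops the tablets. Section 10.0 separates leaving treatment, with follow-up permitted, from withdrawing consent, which ends both. Discontinuation in Section 9.1.11 could mean leaving the study only. The toxicity that leads a patient to stop arises during participation, so it belongs on the CRF in any case, and Section 11.0 places the common side effects in the first week. Only new events after study exit are at issue.

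Finally, a comparison confined to the treatment period is a legitimate choice. Section 12.0 allows subjects to buy L-TAMS after the study, so a 30-day tail pooled into the main comparison could include placebo patients taking the active agent.

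What the reply does not answer is that nothing prompts detection after Day 63, and that no route is given for late reports into the safety data.

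**Conclusion.** The mismatch is real, and its consequence is limited. The plan undertakes to act on serious events, and in its expedited-reporting steps on all events, for 30 days after the last dose. It closes the CRF before then, schedules no contact, and does not say how late reports join the database. New events after study exit may go undetected, or be reported with no stated route into the safety data.

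The figures of 32% and 81% are shares of calendar days. They do not mean that a third or more of events are lost, and the 81% needs a patient to stop treatment and leave the study on Day 7. The range of about 0.4 to 6 of 60 patients rests wholly on assumed rates. The number of affected events, and any imbalance between arms, cannot be derived from the documents.

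This is a cheap improvement to safety capture rather than a defect that invalidates an analysis.

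**What to change.** - **Section 9.1.11:** reconcile with Sections 11.6 and 11.7 so that CRF recording covers the 30 days after the last dose, at minimum for serious events. State that this includes patients who stop treatment but have not withdrawn consent for follow-up, which also settles what discontinued means there.
- **Section 6.0 and Appendix 1:** add one telephone contact at the end of that period, of the kind already made between visits.
- **Data handling:** say how reports received after study exit enter the database.
- **Section 3.0, Safety Assessments:** state the adverse-event window for the Fisher comparison, and tabulate events after the last dose separately from on-treatment events. Pooling the two is best avoided because subjects may take L-TAMS once the study ends.

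The cost is one short call per patient, so at most 60 calls, together with small changes to the visit section and schedule and the IRB approval that Section 14.7 requires for an amendment. Patients who have withdrawn consent for follow-up cannot be called, so some incompleteness will remain.

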#### **9.1.12 Concomitant Medications**

Concomitant Medications will be documented using the Concomitant Medications form at Baseline and all study visits.

#### **9.1.13 Study Medication Adherence**

Participants will be asked about his/her medication adherence at each appointment. Study personnel will count and record the number of pills in the patient's study medication bottles and provide immediate feedback, reinforcing the behaviors of patients who appear to be taking medications as prescribed and problem-solving with those who appear not to be. Clinicians will review with patients the use of pill-minder boxes, as needed.

#### **9.1.14 Laboratory Test Assessments**

Northwestern Medicine Laboratory will be used for analysis of fasting lab assessments required during the study. Blood will be drawn from each patient at the screening visit, and at end of study as noted in the study Schedule of Events in Appendix 1. The fasting tests will include: Hematology and chemistry panels; pregnancy (women of childbearing potential only), serum creatinine, and urine drug screen (UDS).

Note: At screening and throughout study participation, a positive UDS or blood alcohol screen is not necessarily exclusionary and/or may not require a subject be withdrawn from the study. This decision will be per the discretion of the principal investigator.

A blood sample will be collected and analyzed for plasma Mg2+, Red blood cell Mg2+ (RBC-Mg) and total RBC cell count.

##### **9.1.14.1 Genetic Testing**

All subjects will be consented to obtain a blood sample for genetic studies to search for possible markers for response to MMFS-202-302 in participants with schizophrenia. DNA from patients already studied by the PI will be available for comparison.

#### **9.1.15 EEG Assessments**

Research participants will undergo EEG recording while participating in learning and memory tests at baseline and end of study visits. Prior to the experiment, research participants will be familiarized with EEG and prepared for the EEG recording session. Research staff will inform the research participants about the EEG procedures, and will ask the research participants to perform familiarization activities such as wearing the elastic caps that will be worn during the actual experiment (but without EEG recording) and showing the research participants informational videos and images of other individuals engaged in EEG recording.

After this familiarization process has finished, research participants will be prepared for EEG recording. This involves placing an elastic cap on the head of the research participant. Recording electrodes are embedded within the elastic cap, and these electrodes record the electrical activity of the research participants' brains non-invasively. The EEG apparatus is battery-powered, and poses no serious risk of physical harm to the research participant. Each recording electrode is filled with a non-toxic, hypoallergenic electrolytic gel so that the electrode makes contact with the participant's skin. The gel is injected using a blunt, plastic-tip syringe that poses minimal risk of skin abrasion because it is blunt and made of plastic. Electrodes are also affixed to the cheeks, temple area, and behind the ears using medical-grade tape that can be easily removed after the experiment. Participants then take part in the learning/memory testing during EEG recording. When the experiment is finished, the elastic cap is removed and participants are given the option to either wash the gel out of their hair in a sink provided in

the same laboratory (with help from the research staff as needed), or to simply leave and wash the gel out at home. Participants are then debriefed and dismissed. There are no known lasting physical ramifications of the EEG procedure. The only known risk to the research participant is the mild discomfort associated with wearing the EEG cap and possible frustration with the learning and memory tasks.

Research staff is trained to identify participant discomfort and frustration during the experiment. In response, research staff will adjust the EEG cap for comfort, introduce rest breaks as necessary, and provide positive feedback regarding performance when possible to reduce potential frustration.

